## **6. Procedures Involved**

After consent has been obtained, patients will be randomly assigned to ketorolac group or non-ketorolac group. All patients will receive a similar anesthetic with inhalational induction with the exception of the ketorolac group receiving 0.5mg/kg IV ketorolac at the end of the procedure once hemostasis has been achieved. The PACU nurses, who will be blinded to ketorolac administration, will evaluate the patients using FLACC scores at 10 minutes post-op, 20 minutes post-op and at time of PACU discharge. For patients with a FLACC score of 6-10, morphine 0.05mg/kg will be administered. For patients with FLACC scores of 3-5, morphine 0.025mg/kg will be administered. The total amount of opioid required to obtain a FLACC score of less than 3 will be evaluated as the primary outcome. The secondary outcomes to be evaluated will be PACU FLACC scores, time required in PACU, incidence of post-tonsillectomy bleeding and total pain medications administered during hospital admission.

All patients will undergo inhalational induction with Nitrous Oxide and Sevoflurane. After IV placement, propofol 1-3mg/kg and fentanyl 1mcg/kg will be administered prior to intubation. Immediately after induction, dexamethasone 0.5mg/kg and an IV infusion of acetaminophen 15mg/kg will be administered. During the intra-op course, dexmedetomidine 0.5mcg/kg and odansetron 0.1mg/kg will be given. Patients in the ketorolac group will receive 0.5mg/kg IV, while those in the non-ketorolac group will not receive any.

A rescue dose of Fentanyl 0.5-1mcg/kg IV will be available for administration at the end of the procedure. The decision to administer this will be left to the discretion of the attending anesthesiologist for the case. The choice to give this will be made based on variables including patient's condition and a 20% increase in the heart rate and blood pressure. In PACU, nurses will be blinded to ketorolac administration, but will be informed of all other medications given.

---

**Protocol Title:** Ketorolac as a Strategy for Reducing Post-Operative Opioid Requirement in Children with OSA undergoing Adenotonsillectomy: A Randomized Controlled Trial

---

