## **7. Statistical Analysis Plan**

Descriptive statistics will be calculated for all variables of interest and will include means and standard deviations, medians and ranges, or counts and percentages, as appropriate. Characteristics of subjects who received ketorolac will be compared to those who did not receive ketorolac using Chi-square tests for comparisons of categorical variables (i.e. gender, race, etc.) and two-sample tests or Mann-Whitney tests for continuous variables (i.e. age, apnea hypopnea index, etc.). For binary outcomes, such as post-tonsillectomy bleeding, cohorts will be compared using Chi-square tests. Generalized linear models will be used to compare differences in amount of narcotic among the two tonsillectomy cohorts, adjusting for any differences in patient and surgical characteristics that may exist between the two groups. Statistical significant will be performed using Stata v. 13.1 (College Station, TX).

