## **22. Informed Consent**

Only those patients who meet the Inclusion criteria will be considered as possible study candidates. A thorough discussion between the parents or legal guardian and the principal investigator, or the study coordinator will occur during the study consent process. No study related procedure will occur prior to obtaining appropriate informed consent. Patients will be enrolled consecutively as they present to Children's Healthcare of Atlanta. The parents or legal guardian of the patient will be approached in clinic prior to surgery by the principal investigator, or the study coordinator to discuss the goals, benefits and risks of the project. Written informed consent will be obtained following this discussion. For the occasions when parents do not arrive at the hospital until the day of surgery, they will be approached only if there is sufficient time to allow for their full consideration. One parent even if the other parent is alive, known, competent, reasonably available, and shares legal responsibility for the care and custody of the child.

Patients undergoing emergent/urgent procedures or when there is insufficient time for the parents to thoroughly consider the goals, benefits and risks of this project will not be approached for enrollment.

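### The model for narcotic amount may adjust for surgical variables recorded after randomisation, and its selection rule favours those that the arm has affected

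*Combined protocol and SAP*

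**What the plan says.** Section 7 (Statistical Analysis Plan) gives one model for opioid use: "Generalized linear models will be used to compare differences in amount of narcotic among the two tonsillectomy cohorts". The same sentence then sets the covariates, with the comparison to be made by "adjusting for any differences in patient and surgical characteristics that may exist between the two groups". It is not labelled the primary analysis, but it is the only model that fits the primary outcome in Section 6 (Procedures Involved): "The total amount of opioid required to obtain a FLACC score of less than 3 will be evaluated as the primary outcome". Section 7 names gender, race, age and apnea hypopnea index as characteristics to compare. It names no surgical variable and excludes none.

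On timing, Section 6 says "After consent has been obtained, patients will be randomly assigned to ketorolac group or non-ketorolac group", and Section 22 (Informed Consent) says "The parents or legal guardian of the patient will be approached in clinic prior to surgery". The ketorolac group receives "0.5mg/kg IV ketorolac at the end of the procedure once hemostasis has been achieved"; the other group receives none, and no placebo is described. The only blinding stated is that of "The PACU nurses, who will be blinded to ketorolac administration". Section 6 also makes a rescue fentanyl dose available at the end of the procedure: "The decision to administer this will be left to the discretion of the attending anesthesiologist for the case".

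**The concern.** Randomisation makes the arms comparable on everything fixed before assignment, so a difference in such a variable is chance and adjusting for it is harmless or helpful. A variable recorded after assignment may differ because the arm changed it. Adjusting for it then removes or distorts part of the effect that randomisation was meant to deliver. If it also marks the child's pain sensitivity, it can create an arm difference where there is none.

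Section 7 does not separate the two kinds, and it uses an observed difference as the reason to adjust. That reason finds pre-randomisation variables only by chance, but finds arm-affected variables systematically. At stake is whether the main morphine comparison can be read as the effect of being assigned ketorolac.

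**Working it through.** The plan has no figure of its own to reproduce. The sample size of 120 comes without alpha, power, effect size or SD, and this point does not depend on it.

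**Step 1: order of events.** Sections 6 and 22 give consent, then randomisation, then (most naturally read) surgery, hemostasis, ketorolac and PACU morphine. Candidate surgical characteristics fall into three groups:

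| Variable | Can the arm change it? |
|---|---|
| Planned procedure (tonsillectomy or adenotonsillectomy) | No; normally settled before surgery |
| Operative time, blood loss, time to hemostasis | Not through the drug, which is given later; only if a team that knows the arm behaves differently |
| End-of-case fentanyl | Plausibly; same window as ketorolac, discretionary, prompted partly by heart rate and blood pressure, decided by someone not stated to be blinded |

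**Step 2: formula.** Let *g* be the shift in covariate S caused by the arm (ketorolac minus control), and *k* the within-arm slope of morphine on S. In a linear model, adjusted arm effect = total arm effect − *k* × *g*. If *g* = 0 the bias is zero. Otherwise its sign depends on the signs of both *k* and *g*.

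**Step 3: two illustrations. Every input is an assumption.**

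*A. S marks pain sensitivity and is less frequent on ketorolac.* True saving 0.020 mg/kg, SD 0.028 mg/kg, S present in 39% of controls, correlation *r* with morphine 0.25 to 0.39. Then *k* = *r* × 0.028 / √(0.39 × 0.61) = 0.0144 to 0.0224 mg/kg.

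| Rate of S on ketorolac | *g* | Size of bias, mg/kg | Adjusted saving, mg/kg |
|---|---|---|---|
| 39% | 0 | 0 | 0.020 |
| 29% | −0.10 | 0.0014–0.0022 | 0.018–0.019 |
| 20% | −0.19 | 0.0027–0.0043 | 0.016–0.017 |
| 13% | −0.26 | 0.0037–0.0058 | 0.014–0.016 |

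Simulation agrees, with attenuation of 7% to 31%. With no ketorolac effect and 60 per arm, a nominal 5% test that always adjusts rejects about 5%, 6–8%, 9–14% and 11–22% of the time in the four rows. The spurious estimates point to more morphine on ketorolac, by 0.001 to 0.006 mg/kg.

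*B. S raises morphine and is higher on ketorolac.* In SD units: direct effect −0.5, slope *b* = 0.4, shift *g* = 0.2 or 0.5. Total effect = −0.5 + 0.4*g* = −0.42 or −0.30, and the unadjusted model recovers it. The adjusted estimate is −0.50 in both cases, so the benefit is exaggerated by 0.08 or 0.20. An unmeasured common cause that adds 0.4 × 0.5 = 0.2 to *k* gives −0.5 − 0.2*g* = −0.54 or −0.60, an exaggeration of 0.12 or 0.30. With *g* = 0, adjustment is unbiased and more precise: standard error 0.186 against 0.199, a reduction of 1 − 0.186/0.199 ≈ 7%.

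**Step 4: the selection rule.** Section 7 does not define a difference. Suppose it means p < 0.05 on a chi-square test with 60 per arm. The chance that S is selected is about Φ(|*g*| / √(2p̄(1−p̄)/60) − 1.96), with p̄ the mean of the two rates:

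- 39% v 29%: Φ(0.10/0.0865 − 1.96) = Φ(−0.80) = 21%
- 39% v 20%: Φ(0.19/0.0833 − 1.96) = Φ(0.32) = 63%
- 39% v 13%: Φ(0.26/0.0801 − 1.96) = Φ(1.29) = 90%

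Simulation gives about 21%, 65% and 92%, against 5% for a variable that the arm does not affect. Under this reading the false-rejection rates in illustration A become about 5%, 7–11% and 11–20%.

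**The case against.** A reader might infer that, because surgery follows randomisation, every surgical characteristic is open to the arm and the model is therefore biased. The documents do not support that. Ketorolac is given only after hemostasis, so it cannot act on operative time, blood loss or time to hemostasis. Those are a concern only if an operating team that knows the arm changes its conduct, which the documents neither show nor exclude. This objection stands and confines the point mainly to end-of-case fentanyl.

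Three further objections stand in part.

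- Section 6 places randomisation after consent but not at a stated time relative to the start of surgery. Assignment before surgery is the natural reading, not an explicit statement.
- Fentanyl is an anesthetic decision, and Section 7 does not say that it counts as a surgical characteristic. It does not say otherwise either, and a rule covering any difference leaves the choice to the analyst.
- The figures are conditional. Under the p < 0.05 reading the smallest shift leaves the error rate at about 5%. If fentanyl itself lowers morphine need (assumed −0.02 mg/kg, no direct ketorolac effect), the unadjusted test also rejects, at about 12% and 19% for shifts to 20% and 13%, against 14% and 21% adjusted. So dropping the covariate does not isolate a direct drug effect. It does recover the effect of assignment, which is what randomisation supports.

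It can also be said that the firmer fault in this sentence is the lack of a pre-specified covariate list. That is fair, and one edit can serve both. Pre-specification alone would not be enough, though: a fixed list that included end-of-case fentanyl would carry the same problem.

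**Conclusion.** The point holds in a limited form. As written, Section 7 can admit a post-randomisation variable into the only model for narcotic amount, and its trigger for adjustment favours variables that the arm has shifted. Bias follows only if the arm does shift the covariate. The documents show a plausible route, through discretionary fentanyl and an operating team not stated to be blinded, but no evidence that it operates.

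Neither direction nor size can be established. A reader might take the attenuation in illustration A as the expected result; illustration B, on equally hypothetical inputs, gives exaggeration. The ranges above show what is possible, not what is likely. The case for changing the text is that the ambiguity costs little to remove now, and a reader could not correct for it afterwards.

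**What to change.** In Section 7, replace "adjusting for any differences in patient and surgical characteristics that may exist between the two groups" with a named set of covariates measured before randomisation, for example age, apnea hypopnea index and planned procedure (tonsillectomy or adenotonsillectomy). State that they are adjusted for regardless of observed imbalance. Add that variables arising in the operating room, including end-of-case fentanyl, operative time and blood loss, are tabulated by arm and enter only a labelled sensitivity analysis, not the primary model.

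This takes a few sentences of SAP wording. The downside is a small loss of precision if an operative variable that the arm does not affect predicts morphine: in the no-shift case of illustration B, forgoing a standard error about 7% smaller.

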## **8. Sharing of Results with Participants**

Study results will not be shared with participants.

## **9. Study Timelines**

- The duration of an individual participant's participation in the study.
- The duration anticipated enrolling all study participants.
- The estimated date for the investigators to complete this study (complete primary analyses)

The subject will participate for one day.

## **10. Inclusion and Exclusion Criteria**

### **Inclusion Criteria:**

- Patients 2 years old through 18 years of age
- Diagnosis of sleep disordered breathing or obstructive sleep apnea
- Children undergoing elective tonsillectomy or adenotonsillectomy at Children's Healthcare of Atlanta Egleston location
- Parent or legal guardian willing to participate, and able to understand and sign the provided informed consent
- No known coagulation defect

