#### **5. Study Intervention/Investigational Agent**

Although not indicated for use in the pediatric population, Ketorolac possesses similar efficacy to morphine and other major opioid analgesics, but does not cause respiratory depression and is not associated with nausea and vomiting, both commonly described complications post-adenotonsillectomy. Importantly, when combined with opioids, it is opioid-sparing. This synergistic effect means that a similar level of analgesia is achieved using a lower dose of opioid. Improved quality of analgesia, in addition to reduction of opioid-related adverse effects, makes ketorolac an ideal adjuvant to study in an OSA population. While data remain mixed as to whether ketorolac contributes to increased hemorrhage post-adenotonsillectomy through

inhibition of platelet aggregation and prolonged bleeding time, several studies have recently emerged that are either reassuring or equivocal.

A systematic review and meta-analysis showed that while ketorolac is associated with a five-fold bleeding risk in adults after any surgical procedure, children under 18 were not at a significantly increased risk for bleeding post-tonsillectomy. Another quantitative systematic

review showed that while NSAIDs were equianalgesic when compared with opioids, and the risk of emesis was significantly decreased, the evidence for NSAIDs to increase bleeding risk post-tonsillectomy was equivocal. A recently updated Cochrane study reviewed 15 trials assessing the effect of NSAIDs on bleeding in children undergoing elective tonsillectomy or adenotonsillectomy, which found no significant increased risk of bleeding when NSAIDs are used in pediatric tonsillectomy.

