## **15. Risk to Participants**

The drug that is being tested may not work any better than regular care. 1-10% of patients that take Ketorolac may have:

- Nausea
- Abdominal Pain
- Headaches

Serious, less common risks include:

- Post-procedure bleeding, after tonsil removal (3%), in children with OSA (2%)
- Less than (1%): chance of allergic or anaphylactic reaction.

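### Section 10 admits 18-year-olds, but the only age-bounded ketorolac bleeding evidence in Section 5 reassures for under-18s only, and consent is provided for through a parent or guardian only

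*Combined protocol and SAP*

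**What the plan says.** The first inclusion criterion in Section 10 is "Patients 2 years old through 18 years of age". A later one requires "Parent or legal guardian willing to participate, and able to understand and sign the provided informed consent". The exclusion criteria include a coagulation defect and longstanding NSAID therapy; none concerns age.

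Section 5 gives the bleeding rationale through three reviews:

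- A meta-analysis specific to ketorolac, which reports that "ketorolac is associated with a five-fold bleeding risk in adults after any surgical procedure" while "children under 18 were not at a significantly increased risk for bleeding post-tonsillectomy".
- A quantitative review of NSAIDs as a class, for which "the evidence for NSAIDs to increase bleeding risk post-tonsillectomy was equivocal". No age limit is stated.
- A Cochrane review of NSAIDs in children, which "found no significant increased risk of bleeding when NSAIDs are used in pediatric tonsillectomy". No upper age is stated.

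Section 15 lists bleeding at 3% after tonsil removal and 2% in children with OSA. It does not split these by age and does not repeat the adult figure from Section 5. Section 22 describes a consent discussion with parents or guardians. Adults appear there only in a statement that cognitively impaired adults will not be approached.

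**The concern.** The protocol draws a line at 18 when it argues that ketorolac is acceptable with regard to bleeding, and then sets an age range that crosses that line. An 18-year-old given ketorolac is not covered by the one reassurance that is both specific to the drug and bounded by age. The same sentence reports a raised risk for adults, and the risk section does not carry that statement forward.

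The consent provisions have a matching gap: the text enrols participants aged 18 but makes no arrangement for them to consent for themselves. At stake are the protection of a possibly very small group and the internal consistency of the protocol, not the efficacy result.

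**Working it through.** The documents give no figure to reproduce here; the check is a comparison of text.

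1. **Does the age criterion include 18-year-olds?** Yes, on its ordinary reading. A range that runs through 18 years ends at the 19th birthday. The criterion that refers to children having elective surgery does not define the term by age, so it does not narrow the explicit range.

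2. **Does the ketorolac-specific review cover them?** No. Its reassurance is for children under 18. Its other group is adults, for whom it reports a five-fold risk. As Section 5 describes it, an 18-year-old is either on the adult side or in neither group, and in neither case within the reassured group.

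3. **Do the other two reviews fill the gap?** Not on what is stated. The review without an age limit is called equivocal, so it reassures nobody in particular. The pediatric review is favourable but gives no upper age, so the text does not show whether it includes 18-year-olds. Both concern NSAIDs as a class.

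4. **Is the gap covered elsewhere?** Section 15 gives bleeding rates without an age split and without the adult figure. Neither the exclusion criteria nor any other section contains a justification or an added safeguard for 18-year-olds.

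5. **Is there a consent route for them?** Sections 10 and 22 name only a parent or legal guardian, and Section 14 gives the right to withdraw a participant to parents or an authorised representative. No section provides for a competent 18-year-old to consent.

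6. **Can the size be estimated?** No. It would need the number of 18-year-olds expected, a bleeding rate at that age without ketorolac, and a relative risk for tonsillectomy at that age. The documents give none of the three.

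**The case against.** The best case on the other side is that this is loose wording. The criteria speak of children and require a signing parent or guardian, and Section 22 is written around parents, so the intended population may be minors. The consent form was not available for this review, so what it provides for 18-year-olds cannot be judged. Safeguards also apply to every participant: the coagulation and NSAID exclusions, investigator withdrawal for safety (Section 14) and the half-way bleeding review (Section 19). This bears on how serious the point is. It does not remove the mismatch, because none of it overrides the explicit age range or supplies a rationale for age 18.

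It is also fair to object that the five-fold figure concerns any surgery, not tonsillectomy. The reference list does include a title stating that perioperative ketorolac increases post-tonsillectomy hemorrhage in adults but not in children, so the adult–child contrast is drawn for this operation too. A title gives neither a magnitude nor an age boundary, however.

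Three stronger readings are tempting, and the documents do not support them:

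- **That all the bleeding evidence stops at 18.** Only one of the three reviews carries that limit.
- **That an exposed 18-year-old has a 10–15% risk of bleeding.** This comes from 5 × 2% = 10% and 5 × 3% = 15%. Section 5 does not say whether five-fold is a risk ratio or an odds ratio; as an odds ratio it would give 9.3% to 13.4%. Section 15 does not label its 2–3% as a rate without ketorolac, so multiplying it by five may count the drug effect twice. The figure is also not shown to hold at 18 for this operation.
- **That 18-year-olds would distort the bleeding comparison or the half-way check.** Ages spread evenly over 2 to 18 would give 120/17 = 7.1 participants aged 18, and 1:1 allocation would put about 3.5 of them on ketorolac. The extra expected bleeds would be 3.5 × (0.10 − 0.02) = 0.28 to 3.5 × (0.15 − 0.03) = 0.42, on a base of 60 × 0.02 = 1.2 to 60 × 0.03 = 1.8, or about 23%. Neither the even age spread nor the allocation ratio is in the documents, and the risks are those rejected above. Even on these assumptions the excess is under half an event. A bleeding comparison with so few events is fragile at any age limit, which is a separate matter.

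**Conclusion.** The point holds as an inconsistency between eligibility, safety rationale and consent. Section 10 admits 18-year-olds. The only ketorolac-specific, age-bounded evidence in Section 5 does not reassure for them, the other two reviews give no stated reassurance at that age, and Sections 10 and 22 provide only for parent or guardian consent.

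The conclusion rests on the ordinary reading of the age criterion and on the reviews as Section 5 describes them. It does not rest on any estimate of an 18-year-old's bleeding risk, and no numerical excess should be attached to it. The number affected is unknown and may be very small. The primary outcome, postoperative opioid amount, and its analysis are unaffected. The point is worth correcting because it concerns participant protection and the correction is cheap.

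**What to change.** Reconcile Sections 5, 10, 15 and 22. Either of two routes would do, and the choice is the sponsor's:

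- **Align the upper age limit** in Section 10 with the age range of the cited evidence and with the parental-consent wording. This is a one-line amendment and loses a few candidates at most.
- **Keep 18-year-olds** and add three things: the supporting rationale for including them, in Section 5; the adult bleeding statement, carried from Section 5 (where it already stands) into Section 15; and provision for their own consent in Sections 10 and 22. This costs a few sentences and a check that the consent form matches.

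Neither route changes the sample size or the planned analysis.

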## 1. Study Summary

Project Title	Ketorolac as a Strategy for Reducing Post-Operative Opioid Requirement in Children with OSA undergoing Adenotonsillectomy: A Randomized Controlled Trial
Project Design	This study is designed as a randomized controlled trial with participants assigned to either Ketorolac or Morphine.
Primary Objective	Determine the effect of Ketorolac administration on total postoperative Morphine dosage required to achieve analgesia in children
Secondary Objective(s)	Characterize the effect of intra-operative ketorolac administration on FLACC pain scores and PACU recovery time
Research Intervention(s)/Interactions	Ketorolac or Morphine for post-operative
Study Population	Children's Healthcare of Atlanta- Egleston
Sample Size	120
Study Duration for individual participants	One Day
Study Specific Abbreviations/ Definitions	OSA: Obstructive Sleep Apnea
Funding Source (if any)	Department: Atlanta Gas Light funds

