## 2. Objectives

Our primary aim is to determine the effect of ketorolac administration on total postoperative morphine dosage required to achieve analgesia in children with OSA undergoing adenotonsillectomy. Our secondary aim will be to characterize the effect of intra-operative ketorolac administration on FLACC pain scores and PACU recovery time. The measures we will monitoring are PACU morphine requirements, FLACC pain scores, PACU recovery time, incidence of post-tonsillectomy bleeding and total amount of pain medications administered during hospitalization.

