## 3. Background

Obstructive sleep apnea (OSA) as an indication for adenotonsillectomy has increased significantly over the past ten years, and now has surpassed recurrent tonsillitis as the most

common indication for this procedure. Opioids continue to be the most commonly administered pain medication for these procedures. Studies have shown that patients with OSA have significantly increased sensitivity to opioids that results in post-operative respiratory

depression and apnea when administered via standard opioid dosing protocols. Children with OSA were shown to have a nearly fivefold increase in the odds of developing respiratory complications when compared to their counterparts with tonsillitis. As such, it is imperative that current anesthetic management of children undergoing this procedure remains as safe and effective as possible for this growing population. Ketorolac possesses similar efficacy to morphine without the same incidence of respiratory depression, nausea and vomiting, which are commonly seen post-adenotonsillectomy. Importantly, when combined with opioids, ketorolac is opioid-sparing. This synergistic effect means that a similar level of analgesia is achieved using a lower dose of opioid. However, there continues to be concern about using ketorolac due to the potential risk of post-operative bleeding from anti-platelet activity.

To our knowledge, the use of ketorolac as part of an analgesic regimen has not yet been studied in the specific population of children with OSA undergoing adenotonsillectomy, though they stand to benefit from it the most. In this randomized prospective study, we will determine the effect of ketorolac on the total dose of morphine required to achieve postoperative analgesia in children with OSA undergoing adenotonsillectomy.

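### The title and aim concern children with OSA, but entry also admits sleep disordered breathing and the analysis pools everyone, so the result does not by itself establish an OSA-specific effect

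*Combined protocol and SAP*

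**What the plan says.** **Target population.** The title in Section 1 reads "Ketorolac as a Strategy for Reducing Post-Operative Opioid Requirement in Children with OSA undergoing Adenotonsillectomy: A Randomized Controlled Trial". Section 2 sets the primary aim as the effect on "total postoperative morphine dosage required to achieve analgesia in children with OSA undergoing adenotonsillectomy". Section 3 motivates the trial by stating that "patients with OSA have significantly increased sensitivity to opioids", and claims novelty because ketorolac in an analgesic regimen "has not yet been studied in the specific population of children with OSA undergoing adenotonsillectomy".

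**Population admitted.** The Section 10 inclusion criterion is "Diagnosis of sleep disordered breathing or obstructive sleep apnea". Neither term is defined, and no sleep study or index threshold is required. Neither the exclusion list nor Section 11 removes a child who has sleep disordered breathing but no OSA diagnosis.

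**Analysis.** Section 7 compares the amount of narcotic between the two arms with a generalized linear model, adjusting for patient and surgical characteristics on which the arms differ. OSA severity appears once, among the "continuous variables (i.e. age, apnea hypopnea index, etc" to be compared between arms. No OSA-only estimate, subgroup or interaction is planned. Section 6 describes randomisation to two groups without mentioning stratification.

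**The concern.** The question is asked about one population and answered in a wider one. The protocol's own rationale gives a reason to doubt that the two are interchangeable. If children with OSA are more sensitive to opioids, they may need less postoperative morphine, which is the primary outcome, and the absolute amount that ketorolac can save may then differ too. The plan has no step that would show whether it does.

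What is at stake is the wording of the conclusion. Followed as written, the plan would attach a statement about children with OSA to an average over an unknown mixture. If the basis of the diagnosis is not captured at enrolment, it may not be reliably recoverable later, because Sections 6 and 23 end data collection at discharge.

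**Working it through.** **The plan's own figure.** The total of 120 (Sections 1 and 12) comes with no alpha, power, effect size or SD, so it cannot be reproduced. Everything below is illustration on stated assumptions.

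**1. What the pooled estimate measures.** Let s be the share of participants with OSA.

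Pooled effect = s × (OSA effect) + (1 − s) × (non-OSA effect)

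One pooled number does not identify the OSA effect unless the two effects are equal or s is close to 1. The documents give neither s nor either effect.

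**2. Range of distortion.** The savings in mg/kg are assumed; non-OSA shares of 30% and 50% are shown.

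| Assumed saving: OSA / non-OSA | Pooled, 30% non-OSA | Pooled, 50% non-OSA | Pooled relative to OSA effect |
|---|---|---|---|
| 0.02 / 0.02 | 0.020 | 0.020 | no distortion |
| 0.02 / 0.04 | 0.7 × 0.02 + 0.3 × 0.04 = 0.026 | 0.5 × 0.02 + 0.5 × 0.04 = 0.030 | 30% to 50% too high |
| 0.04 / 0.02 | 0.7 × 0.04 + 0.3 × 0.02 = 0.034 | 0.5 × 0.04 + 0.5 × 0.02 = 0.030 | 15% to 25% too low |

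The distortion can be nil or go either way.

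**3. An extreme case.** Assume no effect in OSA, 0.8 SD in the others, 60 per arm, and a two-sided 5% test. The pooled difference is (1 − s) × 0.8, that is 0.20, 0.40 or 0.60 SD at 75%, 50% or 25% OSA. The chance of a significant pooled result is then 19%, 59% or 91%. This shows only that a positive pooled result is logically compatible with no OSA effect, not that this is likely.

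**4. What an OSA estimate would cost in precision.** The OSA-only interval is wider than the pooled one by a factor of 1/√s: 1/√0.7 = 1.20 and 1/√0.5 = 1.41.

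With 60 per arm, the difference detectable at 80% power is (1.960 + 0.842) × √(2/60) = 0.51 SD. Within the OSA group, 60 is replaced by 60s:

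| OSA share | Detectable difference (SD) | Power for 0.51 SD |
|---|---|---|
| 75% | 0.59 | 68% |
| 50% | 0.72 | 51% |
| 25% | 1.02 | 29% |

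For the interaction, the detectable difference is 2.802 × √(2/(60s) + 2/(60(1 − s))). That is 1.02 SD at 50% OSA and 1.18 SD at 75% or 25%. A non-significant interaction would therefore say little.

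**5. Effect of misclassification.** Entry requires no sleep study, so an untested child may have OSA. Suppose the groups were formed by sleep-study confirmation and 60% of the unconfirmed group truly had OSA. With true savings of 0.02 and 0.04, the mean in that group would be 0.6 × 0.02 + 0.4 × 0.04 = 0.028. The visible contrast shrinks from 0.020 to 0.008. With an unconfirmed share of 30-50%, the true non-OSA share is only 12-20%, and the pooled overstatement falls to 12-20%.

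**The case against.** The strongest reply is that randomisation protects the comparison in whatever population is enrolled, and that the result carries over to OSA if the effect is similar across diagnoses or few children lack OSA. That is correct. A reader might infer that the pooled result cannot support any statement about OSA. The documents do not justify going that far; they show only that the pooled result is not enough on its own.

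Three further replies have force.

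- **The groups are not clearly distinct.** Section 10 defines neither label, and Section 3 contrasts OSA with tonsillitis, never with sleep disordered breathing. It is therefore not established that the additional children fall outside the rationale. A split by sleep-study confirmation would partly reflect who was tested, as step 5 shows.
- **The apnea hypopnea index may do no harm.** A reader might infer that adjusting for the index would drop untested children and cost power. The plan does not say so. The index would enter the model only if the arms differed on it, the handling of missing values is not stated, and the share without a value is unknown.
- **A subgroup result could be misused.** If a favourable OSA estimate were allowed to restore the OSA claim, the trial would gain a second, uncontrolled route to a positive conclusion.

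These replies limit the size of the point and shape the remedy. They do not remove the mismatch between the stated population and the one enrolled and analysed.

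**Conclusion.** The point holds in a limited form. The title, aim and novelty claim refer to OSA, entry is wider, and the analysis does not separate diagnoses. The pooled estimate is valid for children with sleep disordered breathing or OSA, and the plan gives no means of narrowing that to OSA.

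The distortion cannot be sized from the documents. It vanishes with equal effects, becomes negligible as the OSA share approaches 100%, and reaches 30-50% under an assumed twofold difference with 30-50% non-OSA. Nothing in the documents makes the upper figures more likely than zero, so they should not be read as an estimate of bias.

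**What to change.** Keep the entry criteria as they are, and make these changes before any outcome data are examined.

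1. State the aim and the conclusion for children with sleep disordered breathing or OSA, and align the title.
2. Record at enrolment the diagnosis and its basis, in three levels: OSA confirmed by sleep study, OSA diagnosed clinically, or sleep disordered breathing only. State in advance which levels form the OSA group.
3. Include diagnosis as a prespecified covariate in the primary model, whether or not the arms are balanced on it.
4. Report the treatment difference with its 95% CI in the OSA group, and the treatment-by-diagnosis interaction. Label both descriptive and say that neither can turn the trial into a positive one for OSA.
5. If the apnea hypopnea index is not available for all children, use it descriptively only.

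The cost is a small addition to the enrolment data and a few lines in Section 7. The downsides are a less precise OSA-group estimate (interval about 1.2 to 1.4 times wider than the pooled one if 50-70% have OSA) and possible misclassification of untested children, which recording the basis of diagnosis makes visible but does not cure.
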